12. APPENDICES

12.1. Appendix 1: Abbreviations and Trademarks

AE	Adverse Event
ALT	Alanine Aminotransferase
AP	Analysis Population
ANCOVA	Analysis of Covariance
AST	Aspartate Aminotransferase
AUC	Area under concentration-time curve
AUC(0-t)	Area under the concentration-time curve from time zero (pre-dose) to last time of quantifiable concentration within a participant across all treatments
AUC(0-tau)	Area under the concentration-time curve over the dosing interval
BMI	Body Mass Index
BP	Blood Pressure
CAT	COPD Assessment Test
CI	Confidence Interval
Cmax	Maximum observed concentration
CONSORT	Consolidated Standards of Reporting Trials
COPD	Chronic Obstructive Pulmonary Disease
CPK	Creatine phosphokinase
CRF	Case Report Form
CV	Cardiovascular
CWR	Constant Work Rate
CYP3A4	cytochrome P-450 isoenzyme 3A4
DNA	Deoxyribonucleic acid
D-PPAC	Daily PROactive Physical Activity in COPD
DXA	Dual-energy X-ray Absorptiometry
ECG	Electrocardiogram
ESWT	Endurance shuttle walk test
FDA	United States Food and Drug Administration
FEV ₁	The amount of air which can be forcibly exhaled from the lungs in the first second of a forced exhalation
FSH	Follicle Stimulating Hormone
FVC	Forced Vital Capacity
GCP	Good Clinical Practice
GCSP	Global Clinical Safety and Pharmacovigilance
GFR	Glomerular Filtration Rate
GSK	GlaxoSmithKline
HBsAg	Hepatitis B Surface Antigen
IB	Investigator's Brochure
HDL	High-Density Lipoprotein (cholesterol)
HIV	Human Immunodeficiency Virus

ICH	International Conference on Harmonization of Technical Requirements for Registration of Pharmaceuticals for Human Use
IDSL	Integrated Data Standards Library
IEC	Independent Ethics Committee
IMI	Innovative Medicines Initiative
IRB	Institutional Review Board
ISWT	Incremental shuttle walk test
LBM	Lean Body Mass
LDH	Lactate Dehydrogenase
MedDRA	Medical Dictionary for Regulatory Activities
MMRM	Mixed Model Repeated Measures
MSDS	Material Safety Data Sheet
1-RM	1-repetition maximum
PD	Pharmacodynamic
PK	Pharmacokinetic
PGIC	Patient Global Impression of Change
PGRS	Patient Global Rating of Severity
PP	Per Protocol Population
PRO	Patient Reported Outcomes
PSA	Prostate Specific Antigen
QTc	QT interval corrected for heart rate
QTcB	QT interval corrected for heart rate by Bazett's formula
QTcF	QT interval corrected for heart rate by Fridericia's formula
RAP	Reporting and Analysis Plan
SARM	Selective Androgen Receptor Modulator
SAE	Serious Adverse Event
s-CTX	C-terminal telopeptide of type I collagen
SNIP	Sniff Nasal Inspiratory Pressure
s-PINP	Procollagen type I N propeptide
SPPB	Short Physical Performance Battery
SRM	Study Reference Manual
SRT	Safety Review Team
ULN	Upper Limit of Normal (reference range for laboratory)

Trademark Information

Trademarks of the GlaxoSmithKline group of companies	Trademarks not owned by the GlaxoSmithKline group of companies
NONE	Actigraph

12.2. Appendix 2: Contraceptive Guidance and Collection of Pregnancy Information

Definitions

Woman of Childbearing Potential (WOCBP)

A woman is considered fertile following menarche and until becoming post-menopausal unless permanently sterile (see below)

Women in the following categories are not considered WOCBP

1. Premenarchal
2. Premenopausal female with ONE of the following:
 - Documented hysterectomy
 - Documented bilateral salpingectomy
 - Documented bilateral oophorectomy
3. Postmenopausal female
 - A postmenopausal state is defined as no menses for 12 months without an alternative medical cause. A high follicle stimulating hormone (FSH) level in the postmenopausal range may be used to confirm a postmenopausal state in women not using hormonal contraception or hormonal replacement therapy (HRT). However, in the absence of 12 months of amenorrhea, a single FSH measurement is insufficient.
 - Females on HRT and whose menopausal status is in doubt will be required to use one of the non-hormonal highly effective contraception methods if they wish to continue their HRT during the study. Otherwise, they must discontinue HRT to allow confirmation of postmenopausal status before study enrollment.

Contraception Guidance

Female participants

Female participants of childbearing potential are not eligible to participate.

Male participants

- Male participants with female partners of child-bearing potential are eligible to participate if they agree to ONE of the following during the protocol-defined time frame in Section 6.1:
 - Are abstinent from penile-vaginal intercourse as their usual and preferred lifestyle (abstinent on a long term and persistent basis) and agree to remain abstinent. Periodic abstinence (e.g., calendar, ovulation, symptothermal, post-

ovulation methods), declaration of abstinence for the duration of a trial, and withdrawal are not acceptable methods of contraception.

- Agree to use a male condom plus an additional method of contraception with a failure rate of <1% per year as described in [Table 1](#) when having penile-vaginal intercourse with a woman of childbearing potential
- Men with a pregnant or breastfeeding partner must agree to remain abstinent from penile-vaginal intercourse or use a male condom during each episode of penile penetration during the protocol-defined time frame
- Refrain from donating sperm for duration of study and for 4 months from last dose

Table 1 Highly Effective Contraceptive Methods

Highly Effective Contraceptive Methods That Are User Dependent ^a Failure rate of <1% per year when used consistently and correctly.	
Combined (estrogen- and progestogen-containing) hormonal contraception associated with inhibition of ovulation ^b	

 • oral • intravaginal • transdermal 	
Progestogen-only hormonal contraception associated with inhibition of ovulation ^b	

 • injectable 	
Highly Effective Methods That Are User Independent	

 • Implantable progestogen-only hormonal contraception associated with inhibition of ovulation^b • Intrauterine device (IUD) • Intrauterine hormone-releasing system (IUS) • bilateral tubal occlusion 	
Vasectomized partner	

(A vasectomized partner is a highly effective contraception method provided that the partner is the sole male sexual partner of the WOCBP and the absence of sperm has been confirmed. If not, an additional highly effective method of contraception should be used.)
	
Sexual abstinence	

(Sexual abstinence is considered a highly effective method only if defined as refraining from heterosexual intercourse during the entire period of risk associated with the study drug. The reliability of sexual abstinence needs to be evaluated in relation to the duration of the study and the preferred and usual lifestyle of the participant.)
	

NOTES:

- a. Typical use failure rates may differ from those when used consistently and correctly. Use should be consistent with local regulations regarding the use of contraceptive methods for participants in clinical studies.
- b. Hormonal contraception may be susceptible to interaction with the study drug, which may reduce the efficacy of the contraceptive method. In this case two highly effective methods of contraception should be utilized during the treatment period and for at least 125 days, corresponding to time needed to eliminate study treatment plus 30 days for study treatments with genotoxic potential] after the last dose of study treatment

Collection of Pregnancy Information**Male participants with partners who become pregnant**

- Investigator will attempt to collect pregnancy information on any male participant's female partner of a male study participant who becomes pregnant while participating in this study. This applies only to participants who receive study treatment.
- After obtaining the necessary signed informed consent from the pregnant female partner directly, the investigator will record pregnancy information on the appropriate form and submit it to GSK within 24 hours of learning of the partner's pregnancy.
- Partner will also be followed to determine the outcome of the pregnancy. Information on the status of the mother and child will be forwarded to GSK
- Generally, follow-up will be no longer than 6 to 8 weeks following the estimated delivery date. Any termination of the pregnancy will be reported regardless of fetal status (presence or absence of anomalies) or indication for procedure.

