6.1. Inclusion Criteria

Participants are eligible to be included in the study only if all of the following criteria apply:

1. Participant must be 50 to 75 years of age inclusive, at the time of signing the informed consent.
2. Male and/or female:

a. Male participants:

A male participant with a partner who is a woman of child bearing potential (WOCPB) must agree to use contraception as detailed in [Appendix 2](#) of this protocol during the treatment period and for at least 5 half-lives of study medication have passed after the last ingested dose [125 days, corresponding to time needed to eliminate study treatment for both genotoxic and teratogenic study treatments *plus* an additional 90 days (a spermatogenesis cycle) for study treatments with genotoxic potential] after the last dose of study treatment and refrain from donating sperm during this period.

b. Female participants:

A female participant is eligible to participate if she is post-menopausal and not a woman of childbearing potential (WOCBP) as defined in [Appendix 2](#). Note: Postmenopausal is defined as 12 months of spontaneous amenorrhea [in questionable

cases a blood sample with simultaneous follicle stimulating hormone (FSH) levels consistent with menopause (refer to laboratory reference ranges for confirmatory levels), or be >60 years of age].

3. Confirmed diagnosis of COPD in accordance with the ATS/ERS criteria [Celli, 2004] with a post-bronchodilator FEV₁/ forced vital capacity (FVC) < 0.70 AND 30% ≤ FEV₁%predicted ≤65% of predicted normal value calculated at Screen using the Quanjer reference equation [Quanjer, 2012].
4. Short Physical Performance Battery (SPPB) with ALL of the following:
 - Timed chair stand score ≥1 AND ≤3
 - No score of “0” on any component of the SPPB (i.e., gait speed, balance, or timed chair stand)
5. Body Mass Index (BMI) within the range 18 - 32kg/ m² (inclusive), where BMI = (weight in kg) / (height in meters)²
6. Current smokers OR former smokers with a cigarette smoking history of ≥10 pack years (1 pack year =20 cigarettes smoked per day for 1 year or equivalent). Former smokers are defined as those who have stopped smoking for at least 6 months prior to Baseline.
7. Participants must be able to read and write in the language used for the provided electronic diary and be able to operate an electronic device to a level that allows them to complete an electronic diary on a daily basis.

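### The HRT bullet in Protocol Appendix 2 provides for women of unconfirmed menopausal status on contraception, a route that inclusion criterion 2b does not allow

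*Protocol*

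**What the plan says.** Section 6.1, criterion 2b: "A female participant is eligible to participate if she is post-menopausal and not a woman of childbearing potential (WOCBP) as defined in" Appendix 2. Its note adds: "Postmenopausal is defined as 12 months of spontaneous amenorrhea". Questionable cases are settled by an FSH level consistent with menopause or by age over 60. The criterion offers women no contraception alternative.

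Appendix 2 defines childbearing potential. Under the line "Women in the following categories are not considered WOCBP", item 3 covers the postmenopausal female, and one of its bullets reads: "Females on HRT and whose menopausal status is in doubt will be required to use one of the non-hormonal highly effective contraception methods". The duty applies on one condition, which the bullet words as "if they wish to continue their HRT during the study". For the alternative case it says: "Otherwise, they must discontinue HRT to allow confirmation of postmenopausal status before study enrollment".

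Later in the same appendix, under Contraception Guidance: "Female participants of childbearing potential are not eligible to participate".

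Other sections agree with that line. Section 3.3.1 lists post-menopausal status of all women as a mitigation for reproductive effects. Section 7.3 assigns treatment to men and post-menopausal women only. Section 9.3.6 excludes women of childbearing potential.

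**The concern.** Criterion 2b sends the site to Appendix 2 for the definition it must apply. There the site finds a bullet telling it how to handle a woman on HRT whose menopausal status is unknown: put her on non-hormonal contraception and let her stay on HRT. A site following the cross-reference could take this as permission to enrol her. A site applying 2b alone would turn the same woman away.

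What is at stake is foetal safety and consistent eligibility across sites. Section 3.3.1 names a foetal risk from exposure during reproductive differentiation. The protocol is otherwise built for a trial with no fertile women:

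- The Schedule of Activities and Appendix 6 list no pregnancy test.
- The contraception period in 6.1 is written for men.
- The pregnancy-information procedure in Appendix 2 covers only the partners of male participants.

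There is little to fall back on if such a woman were enrolled.

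**Working it through.** The plan states no figure on this point, so the check is mainly a comparison of text.

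**Step 1: what the bullet does.** It has two branches. In the first, she continues HRT during the study and uses non-hormonal highly effective contraception. In the second, introduced as the alternative, she stops HRT so that menopause can be confirmed before enrolment. Confirmation belongs only to the second branch. The first therefore presupposes a participant whose menopause has not been confirmed. This is current text, not amendment-log text.

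**Step 2: whether she can meet criterion 2b while on HRT.**
- Twelve months of spontaneous amenorrhoea: by assumption not established, since her status is in doubt.
- FSH: Appendix 2 limits FSH confirmation to women not using hormonal contraception or HRT.
- Age over 60: this settles the question for women above 60.

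With entry limited to ages 50 to 75, the conflict is confined to women aged 50 to 60 on HRT with unconfirmed status. They cannot meet 2b without stopping HRT.

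**Step 3: whether another rule removes the conflict.** Section 7.7 allows any therapy not specifically prohibited, and HRT is not named there. Exclusion 9 does not name it either, although its list is open-ended. Neither rule clearly resolves the point.

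**Step 4: size of the residual risk, if a woman were enrolled under the bullet.** Inputs:
- Failure rate: below 1% per year. Appendix 2 refers to "an additional method of contraception with a failure rate of <1% per year as described in" Table 1; the phrase comes from the guidance for male participants. I assume the same rate for a woman using a Table 1 method consistently and correctly.
- Dosing: 13 weeks (Synopsis), 13 × 7 = 91 days.
- Half-life: 5 to 8 days (Section 5.5). Five half-lives, the elimination rule in criterion 2a, give 5 × 5 = 25 to 5 × 8 = 40 days.

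Risk per woman = annual rate × days at risk / 365:
- dosing plus 25 days: 0.01 × 116/365 = 0.0032, so under about 0.32%
- dosing plus 40 days: 0.01 × 131/365 = 0.0036, so under about 0.36%

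Note a to Table 1 warns that failure rates in typical use may differ, so neither figure is a bound for typical use. Neither takes credit for lower fertility at this age.

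**The case against.** The strongest reply is that the bullet never says she is eligible. Eligibility is set by 6.1, where being post-menopausal and not being of childbearing potential are separate tests. Classing her as not of childbearing potential meets only the second. The list in Appendix 2 is plainly not an entry list, since it also names premenarchal girls and premenopausal women after hysterectomy, neither of whom can enter this trial. Section 6 bars deviations from the criteria, Section 9 bars waivers, and Section 7.3 assigns treatment only to post-menopausal women. On this view the bullet is general wording left in a definition, and a careful site would reject her.

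Most of this stands. A reader might infer that the protocol opens the trial to women of childbearing potential; the documents do not support that, because 2b's own menopausal test still excludes this woman. Nor does doubtful status prove fertility. The statements in 3.3.1, 7.3 and 9.3.6 do not mention HRT. They bear on her because Appendix 2 treats a woman as fertile until she is post-menopausal, and she has not shown that she is. If a site accepts the bullet's placement under the non-childbearing heading, the exclusions worded by childbearing potential no longer catch her, so counting statements for and against would not measure the strength of the conflict.

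What the reply does not remove is that the bullet speaks of HRT during the study, in contrast to a branch that confirms status before enrolment. Read plainly, it describes a participant, and it sits in the definition that 2b tells the site to use.

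**Conclusion.** The point holds as an internal inconsistency with low practical risk. Appendix 2 provides for a woman on HRT, on contraception and without confirmed menopause. Criterion 2b, Sections 3.3.1, 7.3 and 9.3.6, and Appendix 2's own ineligibility line allow no such route. Sites have two conflicting instructions, and the governing criterion gives the right answer.

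The affected group is narrow, and the documents give no count of such women. Women with 12 months of spontaneous amenorrhoea, or over 60 under 6.1, are not affected.

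A reader might scale the 1% annual rate to the 91 dosing days and treat the result, 0.01 × 91/365 or about 0.25%, as a ceiling. It is not one: it leaves out 25 to 40 days of elimination and assumes consistent and correct use. The better figure is under about 0.36% per woman, on the same assumption about use.

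No endpoint, sample size or planned analysis changes.

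**What to change.** Delete the option to continue HRT on contraception and replace the Appendix 2 bullet with wording such as:

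> Women aged 60 or under who use HRT and whose menopausal status is uncertain must stop HRT so that postmenopausal status can be confirmed under Section 6.1 before enrolment. If it is not confirmed, they are not eligible. Women over 60 are handled under Section 6.1.

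The age clause is needed. Without it the bullet would make women over 60 stop HRT when criterion 2b does not require it.

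The cost is an edit to one bullet, with no change to visits or procedures. A few HRT users will have to stop HRT or will not be enrolled, which criterion 2b already implies.

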Risks to women and foetal risk	Risks to women of possible androgenic effects from exposure to study compound by handling or by seminal exposure. In pregnant women, risk of exposure to compound during period of fetal reproductive differentiation.	Women who are not post-menopausal should avoid handling or ingestion of the study medication (capsules). Male participants should always use condom with female partners of childbearing potential. Sites to confirm compliance with guidelines by participants at each study visit.
Increase in absolute (not relative) heart weight	There is a theoretical risk that the anabolic effects of GSK2881078 are not only selective for striated skeletal muscle, and that there is an increase in cardiac muscle size. There are no pre-clinical or clinical data to support this risk.	Cardiac MRI will be carried out on a small subset of patients; the scan will be used to evaluate changes from baseline in cardiac size, structure and function in the treatment arm.
Study Procedures		
Risk of cardiac angina from incremental or endurance shuttle walk exercise tests	There is high incidence of cardiovascular comorbidity in COPD; undiagnosed disease may manifest during exercise tests	Physical exam, medical history and baseline ECGs will assess cardiovascular risk. Participants with a history of unstable angina will be excluded. Exercise tests will only be carried out under the supervision of suitably trained study personnel as detailed in the SRM.
Other		
None		

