A physical activity monitor will be worn for 7 days at screening for eligible participants, 7 days after the Day -9 visit, for 7 days after the Day 56 visit, and for 7 days following the day 80 visit. During those periods, participants will rate their physical activity on a daily basis by completing the PROactive eDiary. In addition, participants will be asked to complete additional questionnaires CAT which assesses the impact of COPD on a patient's life, Patient Global Rating of Severity (PGRS), Patient Global Impression of Change (PGIC) during scheduled clinic visits as specified in the SoA Time and Events table (Section 2).

Participants will return to the clinic for a follow-up visit 42 days (± 7 days) after the final dose of study treatment to undergo safety evaluations and final functional assessments. In addition, all remaining study medication that was not returned at the last treatment visit (i.e., Day 90) will be returned to the clinical unit for final drug accountability.

The study duration, including screening and follow-up, is not expected to exceed 6 months for participants in the study.

Unblinded data will be reviewed in-stream by the GSK clinical study team and the safety review team (SRT). If, at any time, the 2.0 mg dose in men or the 1.0 mg dose in women, has a safety signal of clinical concern, treatment will be stopped.

An interim analysis for the assessment of futility is planned. It is anticipated that a formal declaration of futility would not be made before at least 10 participants per group have completed dosing and all key study assessments. However, if at any time it is determined that the probability of a successful outcome is sufficiently low, recruitment could be stopped. The primary endpoint for assessment of futility is strength. However, the decision to continue or stop recruitment will be made by the unblinded GSK clinical study team and Safety Review Team (SRT) based on the evaluation of all available safety, efficacy, and tolerability data. Such decisions will be based on the totality of the data (including strength, lean mass, function, safety, and tolerability). See Section 10 for more detail. The feasibility of making a decision to stop recruitment based on a futility analysis will be dependent on the recruitment rate. Futility will be evaluated separately for female and male participants.

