5.3. Participant and Study Completion

A participant is considered to have completed the study if they have completed all phases of the study including the follow-up visit.

The end of the study is defined as the last participant's last visit.

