9.3.1. Time Period and Frequency for Collecting AE and SAE Information

- All SAEs will be collected from start of treatment until the follow-up visit at the time points specified in the SoA (Section 2).
- All AEs will be collected from the start of treatment until the follow-up visit at the time points specified in the SoA (Section 2).
- Medical occurrences that begin before the start of study treatment but after obtaining informed consent will be recorded on the Medical History/Current Medical Conditions section of the CRF not the AE section.
- All SAEs will be recorded and reported to the sponsor or designee within 24 hours, as indicated in [Appendix 5](#). The investigator will submit any updated SAE data to the sponsor within 24 hours of it being available.
- Investigators are not obligated to actively seek AEs or SAEs in former study participants. However, if the investigator learns of any SAE, including a death, at any time after a participant has been discharged from the study, and he/she considers the event to be reasonably related to the study treatment or study participation, the investigator must promptly notify the sponsor.
- The method of recording, evaluating, and assessing causality of AEs and SAEs and the procedures for completing and transmitting SAE reports are provided in [Appendix 5](#).

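### Partner pregnancies are actively collected only up to the follow-up visit, about 42 days after the last dose, although male contraception is required for 125 days

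*Protocol*

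**What the plan says.** **Collection rule.** Protocol Appendix 2 (Section 12.2) has the investigator try to obtain pregnancy information on a "female partner of a male study participant who becomes pregnant while participating in this study". It adds: "This applies only to participants who receive study treatment". It names no period after participation. Once a pregnancy is captured, the partner is followed to the outcome.

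**End of participation.** Section 5.3: "A participant is considered to have completed the study if they have completed all phases of the study including the follow-up visit". Section 5.1 times that visit: "Participants will return to the clinic for a follow-up visit 42 days (± 7 days) after the final dose of study treatment".

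**Contraception period.** Inclusion criterion 2a in Section 6.1 covers the treatment period and then "125 days, corresponding to time needed to eliminate study treatment for both genotoxic and teratogenic study treatments", with a further 90 days for a spermatogenesis cycle where a treatment has genotoxic potential. The 125 days run from the last dose.

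**Stated risk.** Section 3.3.1 lists exposure of women through handling or semen, and adds: "In pregnant women, risk of exposure to compound during period of fetal reproductive differentiation". The same table reports effects on male fertility and on male-mediated development in a rat study. The mitigation is for sites to confirm compliance at each study visit.

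**Other reporting routes.** Section 9.3.6 tells the investigator to inform the sponsor of a reported pregnancy and to follow Appendix 2. It sets no end date, and it classes abnormal outcomes as serious adverse events. Section 9.3.1 stops routine collection of adverse and serious adverse events at the follow-up visit. After that, "Investigators are not obligated to actively seek AEs or SAEs in former study participants", but a serious event that the site learns of and considers reasonably related must still be notified.

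**The concern.** By binding men to contraception for 125 days after dosing, the protocol treats a conception in that period as one to be avoided. A partner pregnancy in the same period is the failure of that measure, and so the event a safety plan would want recorded. The collection sentence stops earlier, when the man's participation stops. No visit is scheduled after the follow-up visit, so for the rest of the period contraception is required but compliance is not checked, and no stated procedure seeks out a pregnancy.

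At stake is a small number of safety records, not an efficacy estimate. Because events will be few, losing one or two would matter to what can be said about paternal exposure. A conception shortly before the follow-up visit may also be recognised only after it.

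**Working it through.** **Inputs**

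| Quantity | Value | Source |
|---|---|---|
| Collection period | while participating; nothing later named | Protocol Appendix 2 |
| End of participation | follow-up visit | Protocol 5.3 |
| Follow-up visit | 42 days after last dose, range 35 to 49 | Protocol 5.1 |
| Contraception after last dose | 125 days | Protocol 6.1 |
| Spermatogenesis allowance | 90 days | Protocol 6.1 |
| Half-life | 5 to 8 days | Protocol 5.5 |
| Treatment period | about 90 days | Protocol Schedule of Activities |

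**Step 1. Reproduce the 125 days.** Formula: 5 × half-life + 90.
- Half-life 7 days: 5 × 7 + 90 = 125. The stated figure is reproduced.
- Half-life 5 to 8 days: 115 to 130.

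**Step 2. Uncovered post-dose days.** Formula: 125 − day of the follow-up visit, then divided by 125.
- Visit at day 42: 125 − 42 = 83 days; 83/125 = 66.4%.
- Visit at day 35: 125 − 35 = 90 days; 90/125 = 72.0%.
- Visit at day 49: 125 − 49 = 76 days; 76/125 = 60.8%.

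The Schedule of Activities gives the visit as study days 126 to 140. With the last dose on day 90, that is 36 to 50 days after dosing, leaving 89 to 75 days (71% to 60%). The picture is the same.

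**Step 3. Share of the whole contraception period.** Treatment itself is covered. 90 + 125 = 215 days; 83/215 = 38.6%.

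**Step 4. Which part of the 125 days is uncovered.** By the construction in Step 1, elimination takes 125 − 90 = 35 days and the allowance takes the rest. Five half-lives over the stated range are 5 × 5 = 25 to 5 × 8 = 40 days, all before a visit at day 42. Under first-order decay, the fraction remaining at day 42 is 2^(−42/5) = 0.3% to 2^(−42/8) = 2.6%. Only a visit earlier than day 40 combined with a long half-life leaves part of the elimination phase uncovered: at most 40 − 35 = 5 days, with 2^(−35/8), about 5%, remaining at day 35. The uncovered days therefore lie almost entirely in the spermatogenesis allowance.

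**Step 5. What still operates after the visit.** Section 9.3.6 has no time limit, so a pregnancy that a man volunteers could be passed on and followed. Section 9.3.1 keeps related serious events reportable if the site learns of them, and abnormal outcomes count as serious. Neither prompts anyone to report, and a normal or ongoing pregnancy is not a serious event.

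**The case against.** The strongest reply is that the uncovered days matter less than their number suggests. The exposure named in Section 3.3.1 is exposure to the compound, which elimination largely settles before the nominal visit (Step 4). The remaining days come from an allowance that Section 6.1 ties to genotoxic potential, and no section says that this compound is genotoxic. This stands, and it limits the conclusion. A reader might infer that fetal drug exposures would be under-reported; the documents do not support that. It does not remove the gap: the protocol adopts the 125 days and holds men to them, and its own risk table reports male-mediated developmental effects in rats.

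A second reply is that late pregnancies are not lost. A reader might infer that a conception after the follow-up visit would never be recorded. Sections 9.3.6 and 9.3.1 leave a passive route, so that is too strong. What is missing is an active request to report. Even that can be said only of the visible text, because consent pages were removed before review and may contain such an instruction.

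Third, the end of participation is inferred. Section 5.3 defines completion, not the end of pregnancy reporting, and men keep contraceptive obligations afterwards. The Appendix 2 sentence is also garbled, so loose drafting is as likely as an intended cut-off. That is fair, but the man's time in the study is the only workable reading, and a site following the text would stop there.

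Finally, numbers will be small: at least 50 men, about 25 on active drug, aged 50 to 75, only some with a partner of childbearing potential, and those required to abstain or to use a condom plus a highly effective method. This stands.

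**Conclusion.** The mismatch is real and moderate. About 83 of the 125 post-dose days (66%, range 61% to 72%) fall outside active pregnancy collection, or about 39% of treatment plus 125 days. A reader might take the two-thirds figure as a share of the protocol's whole risk period; it applies only to the part after the last dose, because treatment is covered.

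The size rests on three assumptions: that participation ends at the follow-up visit; that the 125 days in Section 6.1 stand; and that no unseen consent wording already asks men to report later. For a man who stops treatment early the gap may be wider. Section 8.1.3 makes stopping treatment a withdrawal from the study, and Sections 8.1 and 8.2 then ask for the follow-up visit only if possible. The number of men with a partner of childbearing potential is not given, so no event count can be calculated. No efficacy endpoint or analysis is affected.

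**What to change.** Reconcile the Appendix 2 collection sentence with Section 6.1. Define the pregnancies to be collected as those conceived in a partner from the man's first dose to the end of whatever post-dose period Section 6.1 finally states. Record them on the existing form and follow them to outcome as already planned. Add one line to the follow-up visit reminding men to report a partner pregnancy to the site until that date, and state that this also applies to men who stopped treatment early. Check that the consent form matches. No contraception duration is proposed here.

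The same edit should reconcile three neighbouring contradictions, without this review saying which version is right:
- the 125 days are explained with a 90-day addition in Section 6.1 but a 30-day addition in note b to Appendix 2, which would need a half-life of (125 − 30)/5 = 19 days;
- the sperm donation restriction is 125 days in Section 6.1 but 4 months in Appendix 2;
- a pregnancy goes to the sponsor within 2 weeks under Section 9.3.6 but within 24 hours under Appendix 2.

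The cost is about two sentences in Appendix 2, the reminder line and any matching consent wording. No visit, test or staff is added. The downside is an occasional late report after a man's last visit.
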